The table below contains the assumed data for the viral RNA detection simulations. This assumes collection of NP swabs from all enrolled individuals on Study Days 1, 3, 5, 7, 14, and 28.

[figure not shown]

Figure 8. Probability of SARS-CoV-2 viral RNA detection assumed in power/sample size determination

Study Day	1	2	3	4	5	7	10	14	28
NP swab	Y	Y	Y	Y	Y	Y	Y	Y	Y
Placebo arm	100%	95%	88%	80%	71%	52%	25%	10%	0%
EIDD-2801 Rx arm (RD -20%)	100%	75%	68%	60%	51%	32%	5%	0%	0%
EIDD-2801 Rx arm (RD -30%)	100%	65%	58%	50%	41%	22%	0%	0%	0%
EIDD-2801 Rx arm (RD -40%)	100%	55%	48%	40%	31%	12%	0%	0%	0%
EIDD-2801 Rx arm (RD -50%)	100%	45%	38%	30%	21%	2%	0%	0%	0%

Cumulative probability of viral RNA isolation

Assumes treatment starts 3 to 4 days (i.e., 72 to 96 hours) after symptom onset. NP=nasopharyngeal.

*Extrapolated from Chen, J. JI 2020

Abbreviations: D = Day; NP = nasopharyngeal; Rx = treatment; Y = yes.

Power/Sample Size for Parts 2 to 9:

For Parts 2 to 9, no formal statistical hypotheses will be tested. In consideration of analysis of secondary virology endpoints in these dose range finding cohorts, separate power calculations were done for Parts 2 to 9. For Parts 2 to 9, sample size sensitivity was estimated based on the combined study parts to compare the change from baseline in viral RNA between participants treated with EIDD-2801 versus participants treated with placebo. A total 96 participants in the

active group and 32 participants in the placebo group will achieve 83% power to detect a between group difference of at least 0.6 SD in SARS-CoV-2 viral RNA change from baseline with a significance level of 0.05 using a two-sided test.

Participants who receive placebo will be pooled in the final analyses. The between group comparisons assessment of dose and exposure response will be evaluated based on endpoints of time to undetectable SARS-CoV-2 viral RNA and change in viral RNA over time (including viral RNA baseline-normalized AUC through Day 28), and number (%) of subjects with 1, 2 or $\geq 3 \log_{10} viral RNA$ decline over time.

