The distribution of days until SARS-CoV-2 is not detectable can be compared between the two trial arms (drug vs. placebo) using an exact stratified log-rank test. At 0.10 (10%) type I error probability and under the assumptions in Figure 9 and the corresponding table below, there is 90% power if the evaluable sample size is 19 individuals per arm in Part 1. In Part 1, anticipating up to 10% missing data, enrolling n=44 participants (approximately 22 per arm) will provide 90% power for the secondary virologic endpoint of time to non-detectable SARS-CoV-2 in NP swabs. Power was calculated empirically in R version 3.6.2 using 5000 simulated datasets.

[figure not shown]

Figure 9: Probability of detectable SARS-CoV-2 assumed in power/sample size determination

	D1	D2	D3	D4	D5	D7	D10
NP swab	Y	Y	Y	Y	Y	Y	Y
Placebo	100%	85%	70%	55%	40%	10%	0%
arm							
EIDD-	100%	50%	35%	20%	5%	0%	0%
2801 Rx							
arm							

Cumulative probability of infectious virus isolation*

Abbreviations: D = Day; NP = nasopharyngeal; Rx = treatment; Y = yes.

Assumes treatment starts 3 to 4 days (i.e., 72 to 96 hours) after symptom onset. NP=nasopharyngeal.

*Extrapolated from Wolfel, R et al. Nature 2020

Reductions in shedding of SARS-CoV-2 RNA in NP swabs at Treatment Days 3, 5, 7, 14, and 28 will also be compared between arms via stratified Wilcoxon rank-sum tests.

Mutation rate (number of mutations in the viral genome) will be assessed using next generation deep genome sequencing (NGS). Mutation rates will be summarized with descriptive statistics and compared between study arms (drug versus placebo).

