5.5.3. Derived Endpoints

• SARS-CoV-2 RNA

Efficacy Endpoint of SARS-CoV-2 RNA will be converted to log₁₀ scale. Listings will include the values in log₁₀ scale and in the original scale. For SARS-CoV-2 RNA values reported as below the limit of detection/quantification (the lower limit of quantification is 1018 copies/mL), 1017 copies/mL will be used in the analyses.

SARS-COV-2 RNA below the limit of detection/quantification will be considered as undetectable (negative) in the analyses.

• SARS-CoV-2 RNA Rate of Decline

The individual rate of SARS-CoV-2 RNA decline will be derived as Average Area under the Curve minus Baseline (AAUCMB, i.e., the average daily viral load value minus baseline) for the five time intervals of: D1-D3, D1-D5, D1-D7, D1-D14 and D1-D28 using the following formulas:

AAUC =
$$\frac{\sum_{i=1}^{n-1} (t_{i+1} - t_i) (\frac{x_{i+1} + x_i}{2})}{(t_n - t_1)} = \frac{AUC}{(t_n - t_1)}$$
, and
AAUCMB=AAUC – Baseline (x at time i=1)

where, x_i is the data value at the ith time point and t_i is the time value at the ith time point.

• Time to non-detectable SARS-CoV-2 viral RNA in NP swabs based on PCR

Two consecutive undetectable viral RNAs in NP swabs (or one negative with no further followup) will be required to achieve the event. The date of the first undetectable result will be the event date. If the subject only has undetectable viral RNA at the last on study assessment, it will be counted as event at the time of the last assessment. Subjects not achieving the event and who complete the study follow-up will be censored at the last viral RNA assessment. Subjects not achieving the event and dropped out before Day 28 will be censored at Day 28.

Time to un-detectable = Date of Event (Censored) – date of first dose+1

• Time to negativity of infectious virus isolation in NP swabs based on infectious virus isolation determined by isolation in Vero cell line culture

This endpoint will be derived similarly to time to undetectable viral RNAs in NP swabs based on PCR. Infectious virus will be measured at Days 1, 3, 5, and 7 and additional details will be provided in the CSR.

• Time to COVID Symptom Resolution:

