9. EFFICACY ANALYSES

9.1. Efficacy Analyses

SARS-CoV-2 RNA

The actual and change from baseline in SARS-CoV-2 RNA (log 10) will be summarized by treatment and visit in tabular and graphic format using descriptive statistics for each specimen type. Individual SARS-CoV-2 RNA over time will be plotted by treatment.

Treatment comparisons between each active dose group and placebo group in SARS-CoV-2 RNA change from baseline will be analyzed using a mixed model for repeated measures (MMRM) with restricted maximum likelihood estimation and an unstructured covariance matrix. This model corrects for dropout and accounts for the fact that measurements taken on the same subject over time tend to be correlated, by using all available information on subjects within the same covariate set to come up with an estimate of the treatment effect for a dropout free population. The statistical model will be fitted with terms for treatment group, visit, treatment by visit interaction, baseline SARS-CoV-2 RNA and baseline SARS-CoV-2 RNA by Visit interaction. The estimated treatment difference for "Active – Placebo" at each visit will be displayed in the summary of statistical analysis together with the 95% confidence interval and the associated p-value. Least Squares Means for each visit will also be presented with the standard error. Least Squares Means and estimated treatment differences for each visit and the associated 95% confidence interval will be displayed graphically.

Sensitivity analyses will be conducted using an Analysis of Covariance (ANCOVA) model with terms for treatment group and baseline SARS-CoV-2 RNA by each study visit. The estimated treatment difference for "Active – Placebo" at each visit will be displayed in the summary of statistical analysis together with the 95% confidence interval and the associated p-value. Least Squares Means for each visit will also be presented with the standard error. If parametric assumptions are violated, non-parametric tests (e.g., extended Mantel-Haenszel test) may be utilized to provide a p-value for sensitivity analysis.

The number and percent of subjects with SARS-CoV-2 RNA of \leq LLOQ, or SARS-CoV-2 RNA reduction of \geq 1, 2, or 3 log₁₀ from baseline will be presented for each treatment group by visit. P-values for between-group comparison may be included as descriptive statistics using a 2 sample binomial test.

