Time to response un-detectable Viral RNA will be summarized using Kaplan-Meier method. The median time to response and the cumulative probability of response by visit along with the 95% confidence intervals will be provided by treatment group.

The baseline adjusted average area under curve (AAUCMB) through Day 3, Day 5, Day 7, Day 14 and Day 28 will be derived and summarized by treatment group. Between groups comparisons will be performed using an ANCOVA model with terms for treatment group and baseline SARS-CoV-2 RNA. The estimated treatment difference for "Active – Placebo" at each visit will be displayed in the summary of statistical analysis together with the 95% confidence

interval and the associated p-value. Least Squares Means for each visit will also be presented with the standard error.

The number and percent of subjects with negative infectious virus isolation based on qPCR assay will be summarized for each treatment group by visit. P-values for between-group comparison may be included as descriptive statistics using a 2 sample binomial test.

Time to negativity of infectious virus isolation will be summarized using Kaplan-Meier method. The median time to response and the cumulative probability of response by visit along with the 95% confidence intervals will be provided by treatment group.

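### Treating RNA results below the quantification limit as measured values shrinks the estimated drug effect on RNA change, to about 75%, 56% and 36% of its size at Days 3, 5 and 7 under the protocol's planning table

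*SAP*

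**What the plan says.** SAP 5.5.3 states that "the lower limit of quantification is 1018 copies/mL" and that for results below it "1017 copies/mL will be used in the analyses".

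SAP 9.1 analyses change from baseline in log10 RNA "using a mixed model for repeated measures (MMRM) with restricted maximum likelihood estimation and an unstructured covariance matrix". The mean model includes "baseline SARS-CoV-2 RNA and baseline SARS-CoV-2 RNA by Visit interaction". An active-minus-placebo difference with 95% CI and p-value is reported at each visit. A per-visit ANCOVA is the sensitivity analysis. "The baseline adjusted average area under curve (AAUCMB) through Day 3, Day 5, Day 7, Day 14 and Day 28" is also compared by ANCOVA. No censored-data model is planned, and the mean models are not limited to visits where RNA is still measurable.

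Protocol 10.5 gives the sponsor's expected detection rates: "The table below contains the assumed data for the viral RNA detection simulations". The same section equates non-detection with a value below the limit of quantification, so one minus each rate is the expected share of substituted values.

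For Part 1, Protocol 10.7.3.2 says "Reductions in shedding of SARS-CoV-2 RNA in NP swabs at Treatment Days 3, 5, 7, 14, and 28 will also be compared between arms", by stratified Wilcoxon tests. For the pooled analyses, Protocol 10.8 already plans ANCOVA for change from baseline and adjusted AUC.

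**The concern.** A value below the limit says only that RNA is under 1018 copies/mL. Entering it as exactly 1017 cuts off the rest of the decline. If the drug works, more active than placebo samples are cut off, so the mean difference shrinks. The more active the dose, the greater the loss.

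At stake are the secondary RNA-shedding objective (Protocol 1.3.3) and the dose-response reading, which Protocol 10.5 bases partly on RNA change and AUC through Day 28. At late visits there is also a numerical problem, because an unstructured covariance needs residual variation at every visit.

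**Working it through.** **1. The plan's own power figure.** Parts 2-9: 96 v 32, 0.6 SD, two-sided alpha 0.05 (Protocol 10.5, SAP 3.2.1). 0.6/√(1/96 + 1/32) = 2.94, and Φ(2.94 − 1.96) = 0.836. The noncentral t with 126 df gives 0.831. The stated 83% is reproduced, for an outcome with no floor.

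**2. Expected share at the floor** (one minus the detection rates in Protocol 10.5, 30-point risk difference, RD −30%).

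| Day | Placebo | Active |
|---|---|---|
| 3 | 12% | 42% |
| 5 | 29% | 59% |
| 7 | 48% | 78% |
| 14 | 90% | 100% |
| 28 | 100% | 100% |

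At 3:1 allocation about 0.75 × 100% + 0.25 × 90% = 98% are at the floor on Day 14.

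**3. Share of the true difference kept.** Assume log10 RNA is latent normal with common SD σ. If p is the proportion detectable and z = Φ⁻¹(p), the latent mean lies σz above the limit and the mean after substitution lies about σ(pz + φ(z)) above it. The gap between log10(1017) = 3.0073 and log10(1018) = 3.0077 is negligible. Since σ cancels in the ratio, the share kept does not depend on it.

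| Day | z, placebo / active | Latent difference (σ units) | pz + φ(z), placebo / active | Difference after substitution | Kept |
|---|---|---|---|---|---|
| 3 | 1.175 / 0.202 | −0.973 | 1.234 / 0.508 | −0.726 | 75% |
| 5 | 0.553 / −0.228 | −0.781 | 0.735 / 0.296 | −0.440 | 56% |
| 7 | 0.050 / −0.772 | −0.822 | 0.425 / 0.126 | −0.298 | 36% |

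At Day 14, taking the active 0% as 0.5% so that z is finite, about 4% is kept.

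**4. By drug activity.** At Day 7 the same formula gives 42%, 36%, 30% and 20% for RD −20%, −30%, −40% and −50%. At Day 5 it gives 61%, 56% and 51% for RD −20%, −30% and −40%.

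**5. Confidence intervals, by simulation.** The documents give no log10 SD or baseline correlation, so I assume SD 1.5, correlation 0.5 and 20 per arm. At RD −30%, with values floored and baseline-adjusted ANCOVA, 95% CI coverage of the latent difference is about 81%, 58% and 8% at Days 3, 5 and 7. The Day 5 estimate is about −0.66 against a true −1.17; at Day 7 it is −0.45 against −1.23. At the planned 0.6 SD effect, coverage is about 93%, 78% and 34%, and lower with 96 v 32. Repeat runs differ by a few points.

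A Tobit model with the same terms is nearly unbiased on these data, with 93-95% coverage. Its power is 0.74 against 0.66 at Day 5, and 0.65 against 0.56 at Day 7.

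**6. Effect on the planned power.** With a true 0.6 SD effect and 96 v 32, ANCOVA on floored data gives the following (ranges are for a baseline coefficient of 0 or 0.5).

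| Day | Estimate (SD) | Power |
|---|---|---|
| 3 | 0.48-0.49 | 81% |
| 5 | 0.36-0.37 | 75-76% |
| 7 | 0.24-0.25 | 67-68% |
| 14 | 0.04 | 33-37% |

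Power falls less than the estimate because the floor also shrinks the residual SD.

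**7. Day 28.** If every value is at the floor, each change equals 3.007 minus baseline. The baseline-by-visit term fits this exactly, with slope −1, treatment estimate 0 and residual SD about 3e-15. The unstructured covariance is singular and the Day 28 test is undefined. If some participants stay positive (placebo/active, n = 128), exact singularity occurs in about 20% of simulated trials at 2%/1%, about 2% at 5%/2.5%, and none at 10%/5%. Even then the Day 28 residual SD is about 0.2, against 1.0 at Day 3.

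**8. AUC weights through Day 28** (trapezoid formula, SAP 5.5.3). The Day 14 value has weight (7 + 14)/2 = 10.5 days and the Day 28 value 14/2 = 7 days, so together 17.5/27 = 65%. The Day 7 value has (2 + 7)/2 = 4.5 days, or 17%.

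**The case against.** The strongest defence is that the consequences are limited. The primary endpoint uses only whether RNA is below the limit. Parts 2-9 test no formal hypothesis. The bias is toward no effect, and type I error stays near 5% under the null. SAP 9.1 also provides proportions at or below the limit, log10-decline responders, Kaplan-Meier summaries, AUC through Days 3, 5 and 7, and an optional non-parametric p-value. All of this is true, and it bounds the seriousness. None of it corrects the MMRM, ANCOVA or AUC estimates and their intervals.

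Four stronger readings are tempting, and the documents do not support them.

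- *The model must fail at Day 28.* That needs exactly 0% detection in both arms. The table is a planning extrapolation, and Protocol 2.1 cites a median clearance of about 11 days in mild and 21 days in severe disease, so some late positives are plausible. If the MMRM fails, the per-visit ANCOVA still gives Days 3 to 7.
- *The SAP replaced the protocol's rank test throughout.* The Wilcoxon test was the Part 1 method only. Mean models for the pooled analyses were in the protocol.
- *The reported intervals miss the true difference.* Coverage depends on visit, effect size, group size and baseline correlation. It is close to nominal at Day 3 for a 0.6 SD effect.
- *78% of the Day 28 AUC carries no information.* The figure (28 − 7)/27 is interval length. The trapezoid weight of the Day 14 and 28 values is 65%, and half of the placebo arm is still expected to be detectable at Day 7, where the Day 7-14 interval begins.

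A censored model also has limits. Its good coverage above comes from data that meet its own assumption, and no censored repeated-measures model was tested. At RD −50%, 98% of active values are below the limit at Day 7. A dose group of 36 is then entirely censored with probability 0.98^36 = 0.48 (0.67 for a group of 20), and its Tobit effect cannot be estimated.

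**Conclusion.** The concern holds for the secondary RNA-change and AUC analyses. The substitution rule biases these estimates toward no effect if the drug lowers RNA, and compresses dose-response. The loss is modest at Day 3 and large by Day 7. Mean change has almost nothing left to measure at Day 14, and at Day 28 the model is singular under the planning table and near-degenerate if only a few participants remain positive.

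The direction needs only that RNA on active tends to be lower than on placebo. The shares kept need the planning detection rates and latent normality, but no SD. The coverage and Tobit figures also need the assumed SD, correlation and group size. The primary endpoint is unaffected.

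One reporting gap is separate. For Part 1, the SAP drops the stratified Wilcoxon test of RNA reduction without listing this in section 11, although SAP section 1 says that substantial differences from the protocol will be identified.

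**What to change.** In SAP 5.5.3 and 9.1:

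- Treat RNA below 1018 copies/mL as left-censored. Estimate the treatment difference at Days 3, 5 and 7 with a censored-normal model (per-visit Tobit or censored mixed model) with treatment and baseline RNA.
- Where a dose group is wholly or almost wholly below the limit, report the proportion below it and a rank test instead.
- At Days 14 and 28, compare the proportion below the limit and do not model mean change.
- Pre-specify the Wilcoxon test at each visit.
- Make the AUC through Day 7 the main AUC summary, with Days 14 and 28 supportive.
- Keep the planned MMRM and ANCOVA with substitution as a sensitivity analysis.

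In SAP section 11, list the Part 1 change from the stratified Wilcoxon test.

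The cost is SAP wording and some programming, with no new data. The downside is reliance on a normal latent distribution below the limit, which the rank test and the retained substitution analysis help to check.

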4. SELECTION AND ENROLLMENT OF PARTICIPANTS

4.1. Inclusion Criteria

- 4.1.1. Able to provide informed consent prior to initiation of any study procedures.
- 4.1.2. ≥ 18 years of age at Screening.
- 4.1.3. Study treatment is expected to begin within ≤ 168 hours from first symptom onset.
- 4.1.4. Ability to swallow pills
- 4.1.5. Documentation of confirmed active SARS-CoV2 infection, as determined by a molecular or non-molecular ("rapid") test conducted at any clinic or laboratory that has a Clinical Laboratory Improvement Amendments (CLIA) certification or its equivalent from a sample collected ≤96 hours prior to study entry.
- 4.1.6. Experiencing at least one of the following SARS-CoV-2 infection symptoms at the time of enrollment: fever (can be subjective including feeling feverish or having chills) OR signs/symptoms of respiratory illness (including but not limited to upper respiratory congestion, loss of sense of smell or taste, sore throat OR lower respiratory illness cough, shortness of breath).
- 4.1.7. Agrees to not participate in another interventional clinical trial for the treatment of SARS-CoV-2 during the study period (28 days) unless hospitalized.
- 4.1.8. Agrees to not obtain investigational medications outside of the EIDD-2801 study.
- 4.1.9. Agrees to the sampling detailed in the SOE and to comply with study requirements including contraception requirements.

- 4.1.10. A female participant is eligible to participate if she is not pregnant or breastfeeding and at least one of the following conditions applies:
 - Is not a woman of childbearing potential (WOCBP)

OR

- Is a WOCBP and using a contraceptive method that is highly effective (a low user dependency method OR a user-dependent method in combination with a barrier method), or be abstinent from heterosexual intercourse as their preferred and usual lifestyle (abstinent on a long-term and persistent basis), as described in Appendix 2 during the intervention period and for at least 50 days after the last dose of study intervention. The investigator should evaluate the potential for contraceptive method failure (ie, noncompliance, recently initiated) in relationship to the first dose of study intervention.
- A WOCBP must have a negative highly sensitive pregnancy test (serum or urine) within 24 hours before the first dose of study intervention.
- Additional requirements for pregnancy testing during and after study intervention are located in Section 6.2.15.

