6.2.13. Virologic Studies

Detailed instructions for preparation and shipment of virologic samples will be provided in a separate document.

Nasopharyngeal (NP) Swab

NP swabs are required to be collected at all sites at the times indicated in the SOE. The site at which virology testing will be performed (UNC at Chapel Hill) will collect 1 NP swab per timepoint and will divide the sample in preparation for analysis by infectivity versus PCR assay. All other study sites will collect 2 NP swabs (1 per nostril) at each timepoint and 1 swab each will be prepared and shipped for analysis by infectivity versus PCR assay.

At study entry (Day 1), the sample should be collected prior to the first dose of study treatment.

Oropharyngeal (OP) Swab (Optional)

Participants enrolled at the site at which virology testing will be performed (UNC at Chapel Hill) will have an OP swab collected per the SOE. At study entry (Day 1), if performed, the sample should be collected prior to the first dose of study treatment. Participants enrolled at other sites will not have OP swabs collected.

Self-collected Nasal Mid-turbinate Swab (Optional)

Participants enrolled at the site at which virology testing will be performed (UNC at Chapel Hill) will have a nasal mid-turbinate swab collected per the SOE. At study entry (Day 1), if performed, the sample should be collected prior to the first dose of study treatment. Participants enrolled at other sites will not have mid-turbinate swabs collected.

Samples collected for viral assessment may be evaluated for the emergence of antiviral resistance at a future date.

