3.2. Sample Size Considerations

3.2.1. Sample Size Determination

This study is designed to evaluate the antiviral activity of EIDD-2801 by estimating the time (days) until elimination of viral RNA in NP swabs in people who receive EIDD-2801 compared to those who receive a blinded placebo. Kaplan-Meier (KM) estimation will be used with a corresponding exact log-rank test (for Part 1). The median time (days) until first non-detectable SARS-Cov-2 NP swabs will be estimated in each trial arm. Anticipating up to 10% missing data, enrolling n=44 participants total (approximately 22 per arm) in Part 1 will provide 88% power to detect a risk difference (active – placebo) of -35% for the primary endpoint using an alpha=0.10 type I error rate and with viral RNA measured at Days 1, 3, 5, 7, 14, and 28.

For Parts 2 to 9, no formal statistical hypotheses will be tested. In consideration of analysis of secondary virology endpoints in these dose range finding cohorts, separate power calculations were done for Parts 2 to 9. For Parts 2 to 9, sample size sensitivity was estimated based on the combined study parts to compare the change from baseline in viral RNA between participants treated with EIDD-2801 versus participants treated with placebo. A total 96 participants in the

active group and 32 participants in the placebo group will achieve 83% power to detect a between group difference of at least 0.6 SD in SARS-CoV-2 viral RNA change from baseline with a type I error rate of alpha=0.05 using a two-sided test.

The proposed total sample size for the study is up to approximately 172 fully evaluable participants. If participants in a dose group drop out or otherwise have missing or unevaluable primary or key secondary virology endpoint data, additional participants may be enrolled to ensure adequate data at each dose level. The total number of participants to be enrolled will not exceed 204.

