5.3.2. Modified Intent-to-Treat (mITT)

mITT population will include all subjects who are randomized into the study and have at least 1 post baseline viral RNA assessment. Subjects will be analyzed according to the treatment they actually received.

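### A negative pre-dose Day 1 swab can count as viral clearance, and no positive baseline is required, although both stated powers assume 100% positive on Day 1

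*SAP*

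**What the plan says.** SAP 5.5.3 requires two undetectable NP results in a row, or one with nothing after it. "The date of the first undetectable result will be the event date", and time is the event date minus the first-dose date plus 1. RNA below the limit of detection or quantification (1018 copies/mL) is negative. The infectious-virus endpoint is derived in the same way, and "Infectious virus will be measured at Days 1, 3, 5, and 7".

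The Day 1 swab comes before treatment: "At study entry (Day 1), the sample should be collected prior to the first dose of study treatment" (Protocol 6.2.13). The SAP mITT population is "all subjects who are randomized into the study and have at least 1 post baseline viral RNA assessment" (SAP 5.3.2). Protocol 10.6 adds that a baseline value must exist, not that it must be positive.

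Entry rests on an outside molecular or rapid test "from a sample collected ≤96 hours prior to study entry" (Protocol 4.1.5), with treatment up to 168 hours after symptom onset (4.1.3).

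The SAP gives 88% power for RNA at a −35% difference, "with viral RNA measured at Days 1, 3, 5, 7, 14, and 28" (SAP 3.2.1). For culture, Protocol 10.7.3.2 says "there is 90% power if the evaluable sample size is 19 individuals per arm in Part 1". The probability tables behind both (Protocol 10.5 and 10.7.3.2) start at 100% positive on Day 1 in both arms.

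**The concern.** As written, negative swabs on Day 1 (pre-dose) and Day 3 make an event at time 1. Such a participant had nothing left to clear. Randomisation spreads these participants over both arms as tied events at time 1, and they dilute the treatment difference. A participant negative on Day 1 but positive on Day 3 is not an event at time 1, so the share that matters is the one negative on both days.

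The SAP does treat Day 1 as part of the endpoint series. Its imputation tables in 5.6 assign a positive status to a missing baseline when the first later value is positive, for both assays.

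For RNA, what is at stake is the Part 1 log-rank comparison behind the 88%. For culture, it is the protocol's log-rank test and its 90%. The SAP itself plans no time-to-event test for culture ("Time to negativity of infectious virus isolation will be summarized using Kaplan-Meier method", SAP 9.1), so under the SAP the harm there is to the curves and medians.

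**Working it through.** **Inputs**
- 19 evaluable per arm, alpha 0.10, two-sided (Protocol 10.5 and 10.7.3).
- RNA detection, Days 3/5/7/14/28, placebo: 0.88/0.71/0.52/0.10/0 (Protocol 10.5 table). Active at the SAP's −35%, floored at 0: 0.53/0.36/0.17/0/0.
- Culture detection, Days 3/5/7: placebo 0.70/0.40/0.10, active 0.35/0.05/0 (Protocol 10.7.3.2 table); censored after Day 7.
- q, the share negative on both Day 1 and Day 3: not in the documents. Assumed 0 to 30%, equal in the two arms.

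**Reproducing the stated powers (q = 0).** Event times were simulated from these tables and tested with a two-sided permutation log-rank test (5,000 trials, 999 permutations). RNA at −35% on the visit days gives 0.879 (stated 0.88). Culture gives 0.912 (stated 0.90). The protocol's 88% at −30% is reproduced (0.884) only with swabs on all nine days of its table; on the actual visit days it is about 0.78. The SAP's −35% is therefore used below.

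**Adding baseline negatives.** A fraction q in each arm is (a) an event at Day 1, as written; (b) an event at Day 3, if only post-dose swabs count; or (c) removed, if only baseline-positive participants are analysed. There were 4,000 trials per setting with 1,000 permutations each.

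| Assay and rule | q=0 | 5% | 10% | 20% | 30% |
|---|---|---|---|---|---|
| RNA (a) as written | 0.887 | 0.837 | 0.777 | 0.660 | 0.536 |
| RNA (b) post-dose swabs only | 0.885 | 0.850 | 0.812 | 0.727 | 0.622 |
| RNA (c) baseline-positive | 0.886 | 0.868 | 0.855 | 0.809 | 0.754 |
| Culture (a) as written | 0.912 | 0.858 | 0.795 | 0.671 | 0.531 |
| Culture (b) post-dose swabs only | 0.911 | 0.885 | 0.850 | 0.773 | 0.679 |
| Culture (c) baseline-positive | 0.909 | 0.903 | 0.878 | 0.835 | 0.782 |

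The simulation standard error at 0.66 is √(0.66 × 0.34 / 4000) ≈ 0.007. A cross-check with 3,000 trials and 999 permutations gave, as written at 5/10/20/30%, RNA 0.83/0.77/0.65/0.54 and culture 0.87/0.80/0.67/0.55. The asymptotic log-rank test gave RNA 0.84/0.79/0.67/0.55 and culture 0.87/0.81/0.69/0.56.

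**Medians implied by the tables.** With share q, the proportion still positive is (1 − q) × detection, and the median is the first visit where this is at most 0.50.
- RNA, q = 0: placebo 0.52 at Day 7 and 0.10 at Day 14, so Day 14. Active 0.53 at Day 3 and 0.36 at Day 5, so Day 5. Gap 14 − 5 = 9 days.
- RNA, q = 10%: placebo 0.9 × 0.71 = 0.639 at Day 5 and 0.9 × 0.52 = 0.468 at Day 7, so Day 7. Active 0.9 × 0.53 = 0.477, so Day 3. Gap 7 − 3 = 4 days.
- Thresholds: placebo RNA moves to Day 7 above 1 − 0.50/0.52 = 3.8%. Active RNA moves to Day 3 above 1 − 0.50/0.53 = 5.7%. Between the two, as at 5%, the medians are Day 7 and Day 5.
- Culture: placebo Day 5 and active Day 3 become Day 3 and Day 3 above 1 − 0.50/0.70 = 28.6%.

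**The case against.** Several objections are fair.

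- **The medians are not moved by the Day 1 dating.** For q below 50% the curve from Day 3 on is the same whether negatives are events at Day 1 or Day 3. The shift comes from not requiring a positive baseline. This stands, and it is why a rule about post-dose swabs alone is not enough.
- **The move from 9 to 4 days is a visit-grid effect.** Placebo detection on Day 7 is 52%, just above one half. With 19 participants and no negatives, the observed placebo median is already Day 7 or earlier with probability P(Bin(19, 0.52) ≤ 9) = 43%. This also stands: the medians are values implied by the tables, not forecasts.
- **The negative share is unknown.** Participants are symptomatic with a recent positive test, and Protocol 2.1.1 puts median RNA clearance in mild disease at about 11 days, so 20–30% RNA-negative may be high. On the other side, the outside test may be up to 96 hours old, treatment may start at 168 hours where the power tables assume 72–96, and early presenters were scarce (SAP 3.3). The protocol's only culture data, 17% of OP swabs, come from another specimen and do not estimate the NP share.
- **Existing provisions may help.** Extra enrolment is allowed for unevaluable virology data, up to 204, but that term is undefined. Baseline-positive infectivity is a listed subgroup only if data permit. Baseline RNA status is not listed, although other baseline characteristics may be explored. None of these changes the event rule.
- **The culture test is superseded, SAP 3.2.1 lists Day 1 only as a power-calculation visit, and type I error is not inflated.** All true. The loss is of power and interpretability.

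**Conclusion.** The point holds. The event rule admits the pre-dose swab, and neither mITT definition requires anything to clear, while both stated powers assume that everyone starts positive. At 10% and 20% confirmed negative, RNA power as written is 0.78 and 0.66 against the stated 0.88. Post-dose swabs alone would bring it to 0.81 and 0.73, and the baseline-positive restriction to 0.86 and 0.81. At 5% the restriction is worth about 3 points (0.84 to 0.87). Culture behaves alike under the protocol's test. Part of the loss is unavoidable because fewer participants are informative.

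The size rests on the assumed q, equal shares in both arms, the plan's own detection tables and a fixed 19 per arm with no replacement. If q is close to zero, little changes.

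**What to change.** In SAP 5.5.3 and 9.1, analyse each time-to-negativity endpoint in mITT participants who are positive on the pre-dose Day 1 NP sample by that assay (RNA above the lower limit of quantification; culture-positive). State that only post-dose swabs can be the event. Report all-mITT as a sensitivity analysis, also with post-dose swabs only. State that the 88% and 90% powers assume 19 per arm, all positive at baseline. Settle this before the unblinded analysis after Parts 1–6 that SAP 4.1 plans.

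This changes wording only and needs no new data. Selection uses a sample taken before dosing, so the randomised comparison is kept. The costs are a smaller analysed number and a result that speaks for participants with detectable virus at the start rather than for all mITT. The stated power is not fully restored: at 20% negative it is 0.81 for RNA and 0.84 for culture.
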